4.2. Participant Exclusion Criteria

A patient will not be eligible for this trial if he/she fulfils one or more of the following criteria:

1. Patients with a past history or current diagnosis of arterial or venous thromboembolic disease including myocardial infarction, peripheral vascular disease and retinal arterial or venous thrombosis.
2. Diagnosis of acute promyelocytic leukaemia (APML) and undergoing induction chemotherapy
3. Patients with a diagnosis/previous history of veno-occlusive disease (also called sinusoidal obstruction syndrome)
4. Patients with known inherited or acquired prothrombotic disorders e.g.
 - a. Lupus anticoagulant
 - b. Positive antiphospholipids
5. Patients receiving any pro-coagulant agents (e.g. DDAVP, recombinant Factor VIIa or Prothrombin Complex Concentrates (PCC) within 48 hours of enrolment, or with known hypercoagulable state
6. Patients receiving L-asparaginase as part of their current cycle of treatment
7. History of immune thrombocytopenia (ITP), thrombotic thrombocytopenic purpura (TTP) or haemolytic uraemic syndrome (HUS)
8. Patients with overt DIC (See Appendix 3 in the protocol for definition)
9. Patients requiring a platelet transfusion threshold $>10 \times 10^9/L$ at time of randomisation. (This refers to patients who require their platelet count to be maintained at a certain specified level on an ongoing basis, and excludes a transient rise in the threshold due to sepsis.)
10. Patients with a known inherited or acquired bleeding disorder e.g.
 - a. Acquired storage pool deficiency
 - b. Paraproteinaemia with platelet inhibition
11. Patients receiving anticoagulant therapy or anti-platelet therapy
12. Patients with visible haematuria at time of randomisation
13. Patients with anuria (defined as urine output < 10 mls/hr over 24 hours).
14. Patients with severe renal impairment ($eGFR \leq 30$ ml/min/1.73m²)
15. Patients with a previous history of epilepsy, convulsions, fits or seizures
16. Patients who are pregnant or breast-feeding
17. Allergic to tranexamic acid.
18. Patients enrolled in other trials involving platelet transfusions, anti-fibrinolytics, platelet growth factors or other pro-coagulant agents.
19. Patients previously randomised into this trial at any stage of their treatment.

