6.1. Introduction

This trial has an intervention arm and a control arm. These are described in the sections below.

Trial treatment will be started as per randomisation assignment as soon as possible within 24 hours, and no later than 72 hours, of the first recorded platelet count $\leq 30 \times 10^9/L$, or if the participant was admitted with a platelet count already below $30 \times 10^9/L$ as soon as possible within 24 hours, and no later than 72 hours, after the start of chemotherapy or conditioning for a stem cell transplant

The participant's eligibility criteria MUST be rechecked to ensure they are still eligible prior to first administration of the trial treatment.

The period of time between randomisation and initiation of the trial treatment will allow time for pharmacy to prepare and dispense the trial treatment.

During their inpatient stay haematology patients may experience severe nausea and vomiting, diarrhoea, or significant mucositis. This may impair their ability to tolerate or absorb an orally administered medication. Therefore the trial treatment will initially be given by intravenous administration until the participant is well and able to tolerate the oral medication. The treating physician can then switch the medication to its oral formulation. The date on which the participant is switched from IV to oral formulation will be documented. The participant must receive at least one dose of the IV formulation before transferring to oral. Participants can return to IV after commencing oral IMP, this must be documented, but care must be taken to ensure the correct dose is prescribed.

If the participant has not met the stopping criteria when they are ready for discharge oral IMP should be prescribed.

In other patient groups the dose of tranexamic acid is the same whether it is given therapeutically or prophylactically. Due to differences in bioavailability 1g IV is equivalent to 1.5g PO. This dose is similar to the doses given in the three previous RCTs that have been performed (See Investigator Brochure for further information).

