6.2. Interventions

6.2.1. CTIMP to be studied

Tranexamic acid (TXA).

Dose schedule TXA 1g every eight hours IV or 1.5g every eight hours PO.

Comparator or placebo

Placebo (saline) if administration is IV.

Placebo capsule or tablet matched for appearance to TXA if oral.

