6.2.2. Description of Trial Drug

Tranexamic acid (Cyklokapron) is trans-4-(aminomethyl)cyclohexanecarboxylic acid, which acts as an inhibitor of fibrinolysis. At the dose used in this study it is a competitive inhibitor of plasminogen activation. Each 10mL vial contains 1g of tranexamic acid (100mg/mL) as an aqueous solution. Vials should be stored between 15° to 25°C. Do not Freeze. Tranexamic acid Injection is administered by infusion, utilising the usual compatible intravenous vehicles (e.g., Sterile Water for Injection, Sodium Chloride for Injection, 5% Dextrose or Ringer's Injection), or slow IV bolus. Parenteral drug products should be inspected visually for particulate matter and discoloration prior to administration, whenever solution and container permit.

The oral preparation will consist of identical tablets from July 2018 (further details available in the Investigator Brochure).

These will be supplied to the clinical trials pharmacist in containers, from which the pharmacist will dispense the required number (according to the randomisation schedule) for the participant.

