6.2.5. Dose Adjustment of Trial treatment in Renal Insufficiency

Renal impairment

In renal insufficiency leading to a risk of accumulation, the use of tranexamic acid is contraindicated in patients with severe renal impairment. For patients with mild to moderate renal impairment, the dosage of tranexamic acid should be reduced according to the serum creatinine level:

Serum creatinine		Dose IV	Dose PO	Administration
µmol/l	mg/10 ml			
120 to 249	1.35 to 2.82	10 mg/kg BW	15 mg/kg BW	Every 12 hours
250 to 500	2.82 to 5.65	10 mg/kg BW	15 mg/kg BW	Every 24 hours
> 500	> 5.65	5 mg/kg BW	Omit dose	Every 24 hours

Oral suggested doses	If creatinine 120 to 249	If creatinine 250 to 500
Participants < 50 kg	500mg BD	500mg OD
Participants 50 to 83 kg	1g BD	1g OD
Participants 84 to 116 kg	1.5g BD	1.5g OD
Participants > 117 kg	2g BD	2g OD

Hepatic impairment

No dose adjustment is required in patients with hepatic impairment.

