17.6. Acknowledgements

All professionals who have participated in the TREATT trial for a minimum of one year will be listed in the acknowledgements section of the final trial report.

18. Protocol Amendments

Any modifications of the protocol which may impact on the conduct of the study, potential benefit of the participant or may affect participant safety, including changes of study objectives, study design, patient population, sample sizes, study procedures, or significant administrative aspects will require a formal amendment to the protocol. Such amendments will be agreed upon by the TREATT TSC, TMG, and NHSBT, and approved by the Ethics Committee and the Competent Regulatory Authority prior to implementation.

Administrative changes of the protocol are minor amendments that have no effect on the way that the study is conducted. These administrative changes will be agreed by the TREATT TMG and the Ethics Committee will be informed of the minor amendment.

Revision History:

Version	Author	Date	Reason for revision
1.0	Various.	10 th September 2014	Version submitted to REC for ethical approval.

1.1	Various.	24 th October 2014	Responding to the REC comments and to provide greater clarity.
1.2	Various	8 th January 2015	Responding to the MHRA comments and to provide greater clarity
1.3	Various	13 th February 2015	Minor changes following provisional approval from MHRA and to provide greater clarity. Additions with respect to the trial in Australia.
1.4	Various	5 th June 2015	Minor textual amendments and changes to Trial team personnel. Amendment of dose adjustment table to bring it in line with Investigator Brochure.
2.0	Various	27 August 2015	
 • Trial Summary – Recruitment status updated: now open • Section 4.2 (and summary) Reordering of exclusion criteria and Clarification of Exclusion Criterion 9 (previously 12) • Sections 5.5 and 6.2.4 – Addition with regard to (potential) participants admitted to hospital with platelet counts $\leq 30 \times 10^9/L$. or $\leq 50 \times 10^9/L$. • Section 7 Proportion of participants changed to estimated proportion • Section 11.4 – Stopping Rules: Change to wording for clarification • 11.5 – Analysis Plan: proportion changed to Estimated proportion • Section 16.1 – Change in name of Australian Trial Coordinator • 16.3 – Reference to co-opted member of DMC removed as not relevant

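### For creatinine 120 to 249, the renal-adjusted IV dose has no maximum, so it equals the standard 3 g a day at 150 kg and exceeds it above that weight

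*Protocol*

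**What the plan says.** The standard regimen is flat, with no weight term. Protocol 6.2.1 gives "Dose schedule TXA 1g every eight hours IV or 1.5g every eight hours PO", and Protocol 6.1 explains the two amounts: "Due to differences in bioavailability 1g IV is equivalent to 1.5g PO".

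Protocol 6.2.5 covers renal insufficiency, where the stated worry is accumulation. It says the drug is contraindicated in severe impairment and that in mild to moderate impairment "the dosage of tranexamic acid should be reduced according to the serum creatinine level". The main table then sets weight-based doses:

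- Creatinine 120 to 249 µmol/l: 10 mg/kg IV or 15 mg/kg orally, every 12 hours.
- Creatinine 250 to 500: the same amounts, every 24 hours.
- Creatinine above 500: 5 mg/kg IV every 24 hours; the oral dose is omitted.

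No row carries a maximum. A second table, headed "Oral suggested doses", gives fixed oral amounts by weight band for the first two rows. Its top band, "Participants > 117 kg", is 2 g twice daily for creatinine 120 to 249 and 2 g once daily for 250 to 500. There is no corresponding table for IV dosing.

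**The concern.** A weight-based dose that replaces a flat dose must cross it at some weight. Above that weight the adjustment raises the daily dose, although the sentence introducing the table calls for a reduction. The question is whether the crossing lies at a weight a trial participant could have, and whether anything else in the protocol prevents it.

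The IV route matters most because every participant starts on it (Protocol 6.1). Creatinine is rechecked during treatment (Protocol 8.4). A very heavy participant on 3 g a day whose creatinine rises into the 120 to 249 range would, by the table, be moved to the same or a larger daily amount as renal function worsens.

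Two smaller consequences follow for the analysis. The per-protocol criteria in SAP 4.2.1 require the correct dose, and for such a participant the table and the sentence above it disagree about what that is. The trial treatment summary in SAP 5.7 counts reduced frequency with renal impairment as a reason, so a change from 8-hourly to 12-hourly would be listed there even if the daily dose had gone up.

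**Working it through.** The plan states no break-even weight, so there is no figure of its own to reproduce. The inputs are the standard doses (Protocol 6.2.1) and the adjusted doses and intervals (Protocol 6.2.5).

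**Standard daily dose.** IV: 3 × 1,000 = 3,000 mg. Oral: 3 × 1,500 = 4,500 mg.

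**Break-even weight** = standard mg per day ÷ (mg/kg per dose × doses per day).

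- Creatinine 120 to 249, IV: 3,000 ÷ (10 × 2) = 150 kg.
- Creatinine 120 to 249, oral mg/kg column: 4,500 ÷ (15 × 2) = 150 kg.
- Creatinine 250 to 500: IV 3,000 ÷ 10 = 300 kg; oral 4,500 ÷ 15 = 300 kg.
- Creatinine above 500, IV: 3,000 ÷ 5 = 600 kg.

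Only the 120 to 249 row crosses the standard dose at a plausible weight.

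**Daily dose by weight, creatinine 120 to 249.** The percentage change from standard is the same for the IV and oral mg/kg columns.

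| Weight | IV, 20 mg/kg/day | Oral column, 30 mg/kg/day | Against standard |
|---|---|---|---|
| 100 kg | 2.0 g | 3.0 g | −33% |
| 140 kg | 2.8 g | 4.2 g | −7% |
| 150 kg | 3.0 g | 4.5 g | 0% |
| 160 kg | 3.2 g | 4.8 g | +7% |
| 170 kg | 3.4 g | 5.1 g | +13% |

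**Oral weight bands.** The top band gives 2 × 2,000 = 4,000 mg a day, and 4,000 ÷ 4,500 = 0.889, or 11% below standard. The amount is fixed, so when the bands are used the oral dose never reaches standard at any weight.

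**Other limits.** The exclusion list (Protocol 4.2) contains no weight criterion. Its renal criteria are anuria and "Patients with severe renal impairment", the latter defined by eGFR of 30 or less. The discontinuation list (Protocol 6.2.6) includes anuria but no creatinine or eGFR value. No other numerical dosing rule limits the IV amount.

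**What a sufficient IV maximum looks like.** Two doses a day must total less than 3,000 mg, so each must be below 1,500 mg.

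**The case against.** The strongest objection is that a reader might infer that both routes are uncapped. The documents do not support that for oral treatment. The bands convert the mg/kg column into whole 500 mg tablets, and above 117 kg they give 2 g twice daily. They are headed as suggestions, so the oral mg/kg column is not formally overridden, but calling the oral dose unlimited would misdescribe the section. This part of the objection stands, and it confines the firm point to IV.

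A reader might also infer that the reduction fails above 100 kg, since a single 10 mg/kg dose then exceeds 1 g. It does not: with two doses a day instead of three, the daily total at 100 kg is still a third below standard.

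It can further be said that nothing is miscalculated. The row gives 20 mg/kg a day at every weight, against about 43 mg/kg a day (3,000 ÷ 70) for an unadjusted 70 kg participant. That is true, and no harm from the heavier doses is shown. The inconsistency remains, however: at 160 kg the unadjusted regimen is 18.75 mg/kg a day (3,000 ÷ 160), so the participant with impaired renal function receives more than one without.

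Lastly, clinicians may stop trial treatment (Protocol 6.2.6) or depart from it in the participant's interest (Protocol 13.3), and the wording above the table tells them which way to go. This makes an actual overdose less likely, but it supplies no figure to prescribe.

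**Conclusion.** The point holds for IV dosing in the 120 to 249 row. The adjusted daily dose equals the standard at 150 kg and exceeds it above, by 7% at 160 kg and 13% at 170 kg, contrary to the stated purpose of the adjustment. For oral dosing it holds only if the mg/kg column is followed instead of the weight bands.

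The point is minor. It needs a participant of 150 kg or more with creatinine in this range who has not been excluded for severe renal impairment. The documents give no weight distribution, so the number is unknown; it is probably very small and may be zero. A reader might infer a threat to the trial's main result, but the primary analysis keeps participants in their randomised arm whatever dose they received, so it is not affected. At most, membership of the per-protocol set could be unclear for such a participant.

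The conclusion assumes that the table is followed as written. The Investigator Brochure was not available for this review and may carry a maximum that the protocol omits.

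**What to change.** First check the Investigator Brochure. The revision history in Protocol 18 records, for version 1.4, "Amendment of dose adjustment table to bring it in line with Investigator Brochure", so the two should agree and any maximum there should be carried across.

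Then add under the main table: *For creatinine 120 to 249, the adjusted daily dose must remain below the standard daily dose (3 g IV, 4.5 g PO).* The sponsor should state an IV maximum below 1.5 g every 12 hours, and state that the oral weight bands apply.

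The exact IV maximum is a choice. Matching the top oral band through the equivalence in Protocol 6.1 would give 2,000 ÷ 1.5 = 1,333 mg per dose, or 2,667 mg a day (11% below standard). That value would also lower doses from about 133 to 149 kg, where the table already gives some reduction, so it is an option and not a requirement. The rows for 250 to 500 and above 500 need no change.

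One clerical correction belongs with this. A participant of exactly 117 kg falls between the 84 to 116 kg band and the top band. At 15 mg/kg the dose is 1,755 mg, nearest to 2 g in 500 mg steps, so the top band should start at 117 kg inclusive.

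The cost is a short note and one symbol in a protocol table, plus the Brochure check. No participants, visits, procedures or analyses are added.

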6.2.6. Discontinuation of Trial treatment

The trial treatment will be permanently discontinued as soon as any one of the following situations occurs:

1. It has been 30 days since the participant first started the randomised trial treatment.
2. The participant has a spontaneous increase in platelet count from $<30 \times 10^9/L$ to $>50 \times 10^9/L$.
3. The participant has had 3 consecutive days with morning platelet counts $>30 \times 10^9/L$, and no requirement for platelet or granulocyte transfusion, or stem cell transplant.
4. The participant receives open label tranexamic acid, other antifibrinolytic agent or procoagulant drug, (e.g., DDAVP, recombinant Factor VIIa, or Prothrombin Complex Concentrates). Use of these agents will be recorded in trial data.
5. The participant begins anticoagulant or antiplatelet therapy.
6. The participant has visible haematuria.
7. The participant has a diagnosis of thrombosis.
8. The participant becomes anuric (defined as urine output $<10 \text{mls/hr}$ over 24 hours).
9. The participant develops sinusoidal obstructive syndrome (SOS, Veno-occlusive Disease, VOD)

Note: If the trial treatment is discontinued it must not be restarted while the participant remains in the trial.

In addition to the reasons stated above participants may stop treatment early or be stopped early for any of the following reasons:

- Disease progression.
- Unacceptable adverse reaction
- Any change in the participant's condition that justifies the discontinuation of treatment in the opinion of the clinician.
- Withdrawal of consent.

In consenting to the trial, participants are consenting to the trial treatment, trial follow up and data collection. As the participant's participation in the trial is entirely voluntary they may choose to discontinue the trial treatment at any time without penalty or loss of benefits to which they are otherwise entitled. Although the participant is not required to give a reason for discontinuing their trial treatment, a reasonable effort should be made to establish this reason whilst fully respecting the participant's rights.

Participants will remain in the trial for the purpose of follow up and data analysis, unless they withdraw their consent from all stages of the trial, in which case, they should be withdrawn. Data collected up until the time of withdrawal will be retained and included in the analysis.

6.3. Adherence to intervention

Daily trial treatment accountability will be performed. Any unused medication will be collected by the research nurse from the ward (if participant is an inpatient) or participant (if participant is an outpatient) and returned to the local trial pharmacist. The pharmacist will document the amount dispensed and returned for each study participant.

6.4. Concomitant Care

6.4.1. Platelet transfusions

Prophylactic platelet transfusions will be given at threshold counts of less than or equal to $10 \times 10^9/L$. A single adult dose should be given on the same day that a platelet count is recorded as less than or equal to $10 \times 10^9/L$, and continued on a daily basis until the platelet count is greater than $10 \times 10^9/L$.

Therapeutic platelet transfusions may also be given following objective and documented signs or symptoms of bleeding at WHO Grade 2, 3, or 4 or in accordance with the local physicians' usual practice.

Prior to planned invasive procedures; physicians will be allowed to increase the transfusion dose and/or threshold in keeping with their current practice.

Clinicians can exercise discretion to transfuse platelets for any reason should they feel there is a clinical reason to do so; the rationale must be clearly recorded on the daily transfusion data form. There is no justification to prescribe platelet transfusions pre-emptively above the defined threshold, if for example the participant's platelet count appears to be falling just prior to a weekend.

In the UK, recommendations for platelet transfusion practice are provided in the BCSH guidelines (35). All platelet components are leucoreduced, around 80% are collected by apheresis, and common hospital practice is to transfuse ABO and RhD identical platelets. In Australia, relevant guidance is provided in the national Patient Blood Management Guidelines available at <https://www.blood.gov.au/pbm-guidelines>

. The type (apheresis or pooled platelets prepared from whole blood) and the dose of platelet transfusion will not be specified.

If a participant develops platelet refractoriness (defined as two sequential transfusions with a 24 hour platelet increment $< 5 \times 10^9/L$), a serum sample will be drawn for lymphocytotoxic antibodies. If the panel reactive antibody (PRA) is $\geq 20\%$, the participant will be presumed to be alloimmune platelet refractory and may be given either HLA-matched or cross-match compatible platelet transfusions. If the PRA is $< 20\%$, local practice will be followed to treat the refractoriness. The participant will remain in the trial and data will continue to be collected on the participant.

6.4.2. Red Cell Transfusions

As a low haematocrit has been associated with an increased bleeding risk (36-38) a common policy to guide red cell transfusion support according to the BCSH Guidelines (UK) and in Australia the national Patient Blood Management Guidelines will be followed, available at <https://www.blood.gov.au/pbm-guidelines>

. This threshold for red cell transfusion (in the absence of blood loss due to bleeding) will be a Hb value of less than 80g/L.

All transfusion components in the U.K. and Australia, including red cells, are standardised and will conform to national specifications. All allogeneic blood components produced in the U.K. and Australia have been subjected to a pre-storage leucocyte filtration process.

No other medication changes are directed in this protocol, and standard care will otherwise be followed.

6.4.3. Contraception

Women of childbearing potential must use effective contraception while receiving the trial treatment. Examples would include the use of the male or female condom, or diaphragm with spermicide. Women of child bearing potential will be excluded if they are sexually active and not using a reliable form of contraception.

6.4.4. Medications Not Permitted

Whilst in receipt of trial medication, participants must not be given any other antifibrinolytic agent or procoagulant drug, (e.g., DDAVP, recombinant Factor VIIa, or Prothrombin Complex Concentrates), nor open label tranexamic acid.

6.5. Co-enrolment guidelines

Please refer to Section 5.7 for details.

6.6. Ancillary and post-trial care

There is no reason why participants could not be prescribed therapeutic tranexamic acid after completion of study period (this will be recorded).

7. Trial Outcomes

